12 REGISTRATION GUIDELINES

Patients must meet all of the eligibility requirements listed in Section 5 prior to registration.

Study-related screening procedures can only begin once the patient has signed a consent form. Patients must not begin protocol treatment prior to registration.

Treatment should start within 21 working days after registration.

To register eligible patients on study, complete a Clinical Trials Office Patient Registration Form and submit to: [contact].

13 DATA SUBMISSION SCHEDULE

The Case Report Forms (CRFs) are a set of (electronic or paper) forms for each patient that provides a record of the data generated according to the protocol. CRFs should be created prior to the study being initiated and updated (if applicable) when amendments to the protocol are IRB approved. **Data capture should be restricted to endpoints and relevant patient information required for planned manuscripts.** These forms will be completed on an on-going basis during the study. The medical records will be source of verification of the data. During the study, the CRFs will be monitored for completeness, accuracy, legibility, and attention to detail by a member of the Research Compliance Office. The CRFs will be completed by the Investigator or a member of the study team as listed on the Delegation of Duties Log. The data will be reviewed no less than annually by the Data and Safety Monitoring Committee. The Investigator will allow the Data and Safety Monitoring Committee or Research Compliance Office personnel access to the patient source documents, clinical supplies dispensing and storage area, and study documentation for the above-mentioned purpose. The Investigator further agrees to assist the site visitors in their activities.

14 SPECIAL INSTRUCTIONS

14.1 Myriad CCP and HRD Analysis

Either prostate biopsy tissue or radical prostatectomy specimens previously collected at the time of diagnosis and/or surgery will be used for the Myriad CCP and HRD assay. There will not be additional tissue collections for this clinical study. Samples from the respective pathology departments will be submitted to Myriad in accordance with the specimen handling requirements of the commercially available test.

Details about CCP can be found at: <https://polaris.com/polaris-for-physicians/for-pathologists/sample-requirements/>

Details about HRD can be found at: <https://mychoicehrd.com/physicians/>

15 ETHICAL AND REGULATORY CONSIDERATIONS

15.1 Informed consent

Informed consent will be obtained from all research participants prior to performing any study procedures using the most recent IRB-approved version.

15.2 Institutional Review

Study will be approved by the Institutional Review Board of University of Utah.

15.3 Data and Safety Monitoring Plan

A Data and Safety Monitoring Committee (DSMC) is established at Huntsman Cancer Institute (HCI) and approved by the NCI to assure the well-being of patients enrolled on Investigator-Initiated Trials that do not have an outside monitoring review. Roles and responsibilities of the DSMC are set forth in the NCI-approved plan. The activities of this committee include a quarterly review of adverse events including SAEs, important medical events, significant revisions or amendments to the protocol, and approval of cohort/dose escalations. If the DSMC and/or the PI have concerns about unexpected safety issues, the study will be stopped and will not be resumed until the issues are resolved. The DSMC also reviews and approves audit reports generated by the Research Compliance Office.

All **phase II** studies are reviewed by the full committee at each quarterly DSMC meeting. This includes a review of all serious adverse events (SAEs) occurring in patients treated at HCI or its affiliates as well as all grade 3 or greater toxicities for patients on treatment and within 30-day follow-up window (only if possibly, probably, or definitely related).

15.4 Adverse Events / Serious Adverse Events

This study will utilize the CTCAE (NCI Common Terminology Criteria for Adverse Events) Version 4.0 for AE and SAE reporting. An electronic copy of the CTCAE Version 4.0 can be downloaded from:

<http://safetyprofiler-ctep.nci.nih.gov/CTC/CTC.aspx>

15.4.1 Adverse Events (AE)

An adverse event is the appearance or worsening of any undesirable sign, symptom, or medical condition occurring after starting the study drug, even if the event is not considered to be related to study drug. For the purposes of this study, the terms toxicity and adverse event are used interchangeably. Medical conditions/diseases present before starting study drug are only considered adverse events if they worsen after starting study drug. Abnormal laboratory values or test results constitute adverse events only if they induce clinical signs or symptoms, are considered clinically significant, or require therapy.

The collection of all adverse events will begin after the first dose of study treatment and end 30 days after the last dose of study treatment. The collection of treatment-related adverse events will continue until the last study visit (or until new cancer treatment is initiated, if sooner),

Information about all adverse events, whether volunteered by the subject, discovered by investigator questioning, discovered by clinical research coordinator interview, or detected through physical examination, laboratory test or other means, will be collected and recorded and followed as appropriate.

The occurrence of adverse events should be sought by non-directive questioning of the patient at each visit or phone contact during the study. Adverse events also may be detected when they are volunteered by the patient during or between visits or through physical examination, laboratory test, or other assessments. As far as possible, each adverse event should be evaluated to determine:

1. the severity grade based on CTCAE v.4 (grade 1-5)
2. its relationship to Radium-223 or EBRT (definite, probable, possible, unlikely, not related).
3. its duration (start and end dates or if continuing at final exam)
4. action taken (no action taken; study drug dosage adjusted/temporarily interrupted; study drug permanently discontinued due to this adverse event; concomitant medication taken; non-drug therapy given; hospitalization/prolonged hospitalization)
5. whether it constitutes an SAE

All adverse events will be treated appropriately. Such treatment may include changes in study drug treatment as listed in the dose modification section of this protocol (see section 8 for guidance). Once an adverse event is detected, it should be followed until its resolution or if patient's participation on the study is terminated or otherwise discontinued, and assessment should be made at each visit (or more frequently, if necessary) of any changes in severity, the suspected relationship to the study drug, the interventions required to treat it, and the outcome.

Information about common side effects already known about Radium-223 is described in the Drug Information (section 3) and the most recent Investigator Brochure. This

information will be included in the patient informed consent and will be discussed with the patient during the study as needed.

All adverse events will be immediately recorded in the patient research chart.

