1.2.6 Evaluate CTCAE version 4.0 toxicities in the study population
Endpoint: Patients will be monitored for adverse events related to Radium-223 and EBRT using CTCAE criteria.

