No cases of radiation-induced cancer have been reported in reported in clinical trials with Radium-223 dichloride in follow-up of up to three years. However, the radiation dose resulting from therapeutic exposure may result in higher incidence of cancer (e.g., sarcomas of the bone, or leukemia), mutations and a potential for development of hereditary defects.

Bone Marrow Suppression

In the randomized trial, 2% of patients on the Radium Ra-223 dichloride arm experienced bone marrow failure or ongoing pancytopenia compared to no patients treated with placebo. There were two deaths due to bone marrow failure and for 7 of 13 patients treated with Radium Ra-223 dichloride, bone marrow failure was ongoing at the time of death. Among the 13 patients who experienced bone marrow failure, 54% required blood transfusions. Four percent (4%) of patients on the Radium Ra-223 dichloride arm and 2% on the placebo arm permanently discontinued therapy due to bone marrow suppression.

In the randomized trial, deaths related to vascular hemorrhage in association with myelosuppression were observed in 1% of Radium Ra-223 dichloride-treated

patients compared to 0.3% of patients treated with placebo. The incidence of infection-related deaths (2%), serious infections (10%), and febrile neutropenia (<1%) were similar for patients treated with Radium Ra-223 dichloride and placebo.

Myelosuppression; notably thrombocytopenia, neutropenia, pancytopenia, and leukopenia; has been reported in patients treated with Radium Ra-223 dichloride. In the randomized trial, complete blood counts (CBCs) were obtained every 4 weeks prior to each dose and the nadir CBCs and times of recovery were not well characterized. In a separate single-dose phase 1 study of Radium Ra-223 dichloride, neutrophil and platelet count nadirs occurred 2 to 3 weeks after Radium Ra-223 dichloride administration at doses that were up to 1 to 5 times the recommended dose, and most patients recovered approximately 6 to 8 weeks after administration.

In the Radium-233 arm of the Phase 3 clinical trial reported in Parker et al. (2013) 12.7% (76/600) of subjects had grade 3+ anemia, 6.5% (39/600) of subjects had grade 3+ thrombocytopenia, and 2.2% (13/600) of subjects had grade 3+ neutropenia.

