10.4 Stopping Rules

10.4.1 Toxicity: If 6 of the first 8 treated subjects develop 2 or more CTCAE grade 3 toxicities related to study drug, it will be reviewed by the DSMC to determine if the trial will continue.

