11 STATISTICAL CONSIDERATIONS

The primary objective is to determine the hormone-therapy-free survival time for men treated with concurrent EBRT and Radium-223 and determine whether 20% of subjects do not meet the progression endpoint and require ADT at 15 months. The primary outcome is 15 months hormone- (or other systemic) therapy-free survival. The null hypothesis is that 99% of subjects will start systemic therapy within 15 months. The alternative hypothesis is that 80% of subjects will start systemic therapy within 15 months. With 20 evaluable subjects there will be 93% power for this alternative hypothesis using an exact binomial test at the one-sided 0.05 significance level. The null hypothesis will be rejected if 2 or more out of 20 subjects are not placed on systemic therapy within one year.

One of the secondary endpoints is to determine the hormone-therapy-free survival time for men treated with concurrent EBRT and Radium-223 and determine whether it is a 30% risk reduction over the SWOG intermittent ADT historic cohort. This secondary hypothesis will be tested only if the primary null hypothesis is rejected. The outcome for

this secondary hypothesis is 15 month hormone- (or other systemic) therapy-free survival. In 2012 a SWOG cooperative group trial reported that 78% of subjects on intermittent androgen therapy had resumed ADT within 15 months, and this proportion will be used as a null hypothesis. With 20 evaluable subjects, and a null hypothesis that 78% or more of patients will start systemic therapy within 15 months there will be 80% power to detect an alternative hypothesis that 48% or fewer will start systemic therapy within 15 month using an exact binomial test at one-sided alpha =0.05 significance level.

Additional, secondary endpoints are time to first skeletal related event (SRE), overall survival, PSA doubling time, overall survival and toxicities. All secondary endpoints will be evaluated descriptively. Time to first SRE, OS, and PSA doubling time will be analyzed via Kaplan-Meier product limit methods and associated 95% confidence intervals. Toxicities will be tabulated using CTAE version 4.0. The number and proportion of subjects with toxicities will be reported.

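### Asymptomatic, untreated grade 3-4 laboratory changes, chiefly lymphocytopenia and leukopenia, can be absent from the toxicity results because Section 11 plans no table of laboratory grades

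*Combined protocol and SAP*

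**What the plan says.** Secondary objective 1.2.6 is worded "Evaluate CTCAE version 4.0 toxicities in the study population". Section 15.4.1 sets the condition for a laboratory value to enter: "Abnormal laboratory values or test results constitute adverse events only if they induce clinical signs or symptoms, are considered clinically significant, or require therapy". It also states: "For the purposes of this study, the terms toxicity and adverse event are used interchangeably". No CTCAE grade makes a laboratory value an adverse event automatically, and clinical significance is not defined.

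Section 11 gives the whole safety analysis as a CTCAE tabulation followed by "The number and proportion of subjects with toxicities will be reported". It plans no table of graded laboratory values.

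Two other places use the same term. Rule 10.4.1 begins "If 6 of the first 8 treated subjects develop 2 or more CTCAE grade 3 toxicities related to study drug", and the committee review in Section 15.3 covers "all grade 3 or greater toxicities for patients on treatment and within 30-day follow-up window" when at least possibly related.

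The underlying data will exist. Section 8.1.1 requires haematology at baseline and before every Radium-223 dose, the Section 9 calendar schedules haematology and chemistry, and Section 10.3 lists laboratory results among the sources for evaluating safety.

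**The concern.** One judgement by the investigator stands between a measured laboratory grade and the only safety table in the plan. Two men with the same grade 3 lymphocyte count can be recorded differently, one as a toxicity and one as nothing. With 20 men and no control arm, one or two such decisions visibly move a reported percentage.

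Comparison with the background data also suffers. Section 3.1.4 gives haematologic laboratory rates from the randomised Radium-223 trial (Table 2.2) separately from adverse-reaction rates. As Section 11 stands, this trial would produce nothing comparable with Table 2.2. Radium-223 is combined here with external beam treatment to as many as five bone sites, so the blood-count results are among the more useful safety data the trial can give.

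**Working it through.** The plan states no figure on this point, so there is none to reproduce. The check has two parts: whether another section closes the gap, and how large the gap could be.

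**Does another section close it?**

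1. *Section 8.1.1.* Grade 3-4 neutropenia, thrombocytopenia or anaemia delays dosing, and discontinuation follows if it lasts more than 14 days. The pre-dose thresholds cover neutrophils, platelets and haemoglobin. Lymphocytopenia and leukopenia are not named; other toxicities are left to local practice. Nothing says that a delay makes the value an adverse event.
2. *Section 10.3.* Laboratory results are named as a safety source, with no reporting rule or analysis.
3. *Section 15.4.1.* Laboratory tests are named as a means of detecting adverse events, but the condition quoted from that section still decides which values qualify.
4. *Section 13.* Data capture is limited to endpoints and information needed for planned manuscripts, so it is not certain that unreported values are even in the dataset.

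The gap therefore stays open, and it is widest for the two cell lines that force no delay.

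**How many cases could be involved?**

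Inputs are the grade 3-4 rates on Radium-223 in Table 2.2: lymphocytopenia 20% (placebo 7%), anaemia 6%, leukopenia 3%, thrombocytopenia 3%, neutropenia 2%. The sample size is 20 (Section 4.2).

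- Expected lymphocytopenia cases = 20 × p. At p = 0.07 this is 1.4; at p = 0.20 it is 4.0.
- P(at least one) = 1 − (1 − p)^20. At 0.07: 1 − 0.93^20 = 0.77. At 0.20: 1 − 0.80^20 = 0.988.
- Lymphocytopenia or leukopenia at the Radium-223 rates, assuming independence: 1 − 0.80 × 0.97 = 0.224, or 20 × 0.224 = 4.5 men.

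These are men in whom the value would occur. The documents give no basis for estimating what fraction would go unreported.

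**Does it matter for rule 10.4.1?**

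Count every Table 2.2 grade 3-4 cytopenia and treat each as related, which is generous to the rule.

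- Independence: P(none) = 0.94 × 0.80 × 0.97 × 0.97 × 0.98 = 0.693. P(exactly one) = 0.275. P(two or more) = 1 − 0.693 − 0.275 = 0.032. P(at least 6 of 8 men) ≈ 3 × 10⁻⁸.
- Any dependence: the expected number per man is 0.06 + 0.20 + 0.03 + 0.03 + 0.02 = 0.34, so P(two or more) cannot exceed 0.34 / 2 = 0.17. P(at least 6 of 8) is then about 0.0005.

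At the cited rates the rule is practically unreachable even with every value captured, so incomplete capture changes almost nothing there. It would matter only at far higher toxicity. If 60% of men truly had two or more related grade 3 toxicities, capturing 75% of such men would lower the trigger probability from 0.315 to 0.088 (assumed values, for illustration).

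**The case against.** The strongest reply is that the gap is narrow and recoverable. A grade 3-4 neutrophil, platelet or haemoglobin value stops the next dose, and it is hard to see an investigator calling such a value clinically insignificant. Section 15.4.1 itself lists temporary interruption among the actions taken for an adverse event. Blood counts are drawn before every dose, so a laboratory table could still be produced at analysis. This stands, and it confines the point mainly to lymphocytopenia and leukopenia. It does not remove it: no section requires those values to be recorded as adverse events or tabulated.

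A second reply is that adverse-event reporting need not under-count. Section 3.1.4 gives grade 3-4 thrombocytopenia as 6% when reported as an adverse reaction and 3% as a laboratory abnormality. It also says that "12.7% (76/600) of subjects had grade 3+ anemia, 6.5% (39/600) of subjects had grade 3+ thrombocytopenia", against laboratory rates of 6% and 3% in Table 2.2. This stands too. A reader might infer that haematologic toxicity will be systematically under-reported, but the documents do not show that. They show that the two measures differ, which is a reason to report both.

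A third reply is that Table 2.2 comes from castration-resistant patients, some with prior docetaxel, whereas exclusion 5.2.9 bars prior chemotherapy for prostate cancer. Section 3.1.4 reports lower grade 3-4 thrombocytopenia and neutropenia in docetaxel-naive patients (1% and 1%, against 4% and 3% after docetaxel). This is why a range is given and why the 20% rate should not be used alone.

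**Conclusion.** The point holds as a small, cheap improvement. As written, the toxicity results for objective 1.2.6 can omit asymptomatic, untreated grade 3-4 laboratory changes, mainly lymphocytopenia and leukopenia. If the Table 2.2 rates of 7% to 20% carry over, about 1.4 to 4 of 20 men would have grade 3-4 lymphocytopenia, and an unknown share would not appear. The true rate could lie outside that range, because the population differs and external beam treatment is added.

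Two stronger readings are tempting and not supported. One is that the main serious marrow toxicity of Radium-223 will go missing: Section 3.1.4 describes myelosuppression chiefly by thrombocytopenia, neutropenia, pancytopenia and leukopenia. The delay rule makes grade 3-4 thrombocytopenia and neutropenia likely to be reported, and leukopenia, which it does not cover, has a grade 3-4 laboratory rate of only 3%. The other is that the stopping count is undermined: at the cited rates the trigger probability is at most about 0.0005 with full capture, so there is almost nothing to lose.

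**What to change.** In Section 11, alongside the adverse-event table, add a table of worst post-baseline CTCAE grade per man for each gradable haematology and chemistry parameter. Derive it from all scheduled laboratory values, whether or not they were reported as adverse events, and give the number and proportion of men at each grade.

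The cost is one extra table, with no additional blood draws, visits or patients. Because Section 13 restricts data capture, confirm that the blood count and chemistry values are on the case report form; if they are not, they must be added or extracted from the medical record.

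No change to rule 10.4.1 is proposed on this ground. Counting laboratory values there would need a relatedness assessment for each value, which Section 15.4.1 plans only for adverse events, and would gain nothing at the cited rates.

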15.4.2 Serious Adverse Event (SAE)

Information about all serious adverse events will be collected and recorded in compliance with all institutional and government requirements. A serious adverse event is an undesirable sign, symptom, or medical condition that:

- is fatal or life-threatening
- results in persistent or significant disability/incapacity
- is medically significant, i.e., defined as an event that jeopardizes the patient or may require medical or surgical intervention to prevent one of the outcomes listed above
- causes congenital anomaly or birth defect
- requires inpatient hospitalization or prolongation of existing hospitalization, unless hospitalization is for:
 - routine treatment or monitoring of the studied indication, not associated with any deterioration in condition (procedures such as central line placements, paracentesis, pain control)
 - elective or pre-planned treatment for a pre-existing condition that is unrelated to the indication under study and has not worsened since the start of study drug
 - treatment on an emergency outpatient basis for an event not fulfilling any of the definitions of a SAE given above and not resulting in hospital admission
 - social reasons and respite care in the absence of any deterioration in the patient's general condition

The collection of serious adverse events will begin after the first dose of study treatment and end 30 days after the last dose of study treatment. The collection of treatment-related serious adverse events will continue until the last study visit (or until new cancer treatment is initiated, if sooner).

Any death from any cause while a patient is receiving treatment on this protocol or up to 30 days after the last dose of protocol treatment, or any death which occurs more than 30 days after protocol treatment has ended, but which is felt to be treatment related, must be reported.

Toxicities that fall within the definitions listed above must be reported as an SAE regardless if they are felt to be treatment related or not. Toxicities unrelated to treatment that do NOT fall within the definitions above must simply be documented as AEs in the patient research chart.

15.5 SAE Reporting Requirements

SAEs must be reported to the DSMC, the FDA, the IRB, and Bayer according to the requirements described below:

A MedWatch 3500A form must be completed and submitted to [contact] within 1 business day of first knowledge or notification of the event.

DSMC Notifications:

- An HCI Research Compliance Officer (RCO) will process and submit the MedWatch form to the proper DSMC member as necessary for each individual study.
- The RCO will summarize and present all reported SAEs according to the Data and Safety Monitoring Plan at the quarterly DSMC meeting.

FDA Notifications:

- Adverse events occurring during the course of a clinical study that meet the following criteria will be promptly reported to the FDA:
 - Serious
 - Unexpected
 - Definitely, Probably, or Possibly Related to the investigational drug
 - Fatal or life-threatening events that meet the criteria above will be reported within 7 calendar days after first knowledge of the event by the investigator, followed by as complete a report as possible within 8 additional calendar days.
- All other events that meet the criteria above will be reported within 15 calendar days after first knowledge of the event by the investigator.
- The RCO will review the MedWatch report for completeness, accuracy, and applicability to the regulatory reporting requirements.
- The RCO will ensure the complete, accurate, and timely reporting of the event to the FDA.
- The Regulatory Coordinator will submit the report as an amendment to the IND application.
- All other adverse events and safety information not requiring expedited reporting that occur or are collected during the course of the study will be summarized and reported to the FDA through the IND Annual Report.

IRB Notification:

- Events meeting the University of Utah IRB reporting requirements (<http://www.research.utah.edu/irb/>) will be submitted through the IRB's electronic reporting system within 10 working days.

Bayer Notifications:

An ADEERS form (Adverse Event Expedited Reporting System) available at

<http://ctep.cancer.gov/reporting/adeers.html>

OR

A MedWatch form

All reports shall be sent electronically to:

Electronic Mailbox: [contact]

[contact]

Address: Global Pharmacovigilance - USA

Mail only: Bayer HealthCare

[name]

Address: [name]

FDX or UPS only [name] for UPS

